7 rather than detailed, specific steps.

8 a) We will perform quality control and background normalization of the gene array data.

9 b) Expression value estimates will be obtained and quantile normalization and median scaling
10 of the genes will be performed.

11 c) A list of genes up- or down-regulated >2-fold with $p > 0.05$ will be prepared using the
12 following procedure:

- 13 1. For each patient, genes up- or down-regulated >2-fold in the second biopsy
14 compared to the first will be identified.
- 15 2. Lists will be prepared of genes that are up- or down-regulated >2-fold for any of the
16 subjects.
- 17 3. A paired t-test will be used to identify genes from this list that have a p value < 0.05
18 (Difference is not equal to zero).
- 19 4. The subset of the genes in (3) that are up- or down-regulated in >50% of patients in
20 groups defined relapse and/or presence of cirrhosis will be identified.
- 21 5. This procedure will be repeated with $p < 0.01$, but the primary analysis will be
22 based on the genes selected using $p < 0.05$.

23 d) The false discovery rate (FDR) of the t test will be estimated.

24 A more detailed statistical analysis plan will be developed prior to the start of data analysis.

25

26

27

HAZARDS AND DISCOMFORTS

28

The risks and discomforts of frequent phlebotomy.

30 To document stable levels of biochemical and serologic markers of chronic hepatitis and to monitor
31 the effects and toxicities of the combination of peginterferon alfa-2a and the nucleos(t)ide analogue
32 frequent blood sampling will be required. Patients will have between 11 and 12 venipunctures
33 during the study. Each venipuncture will be for approximately 20 to 75 cc of blood. The total amount
34 of blood drawn during an 8 week period will not exceed 10.5 ml/Kg or 550 mls, whichever is smaller.

35

The risks and discomforts of HIV testing.

36

1 Patients will have blood tested for anti-HIV at entry. Mention of anti-HIV is made in the consent form
2 which includes the exact language used in the standard consent form used for anti-HIV testing at the
3 Clinical Center. It is important to test for HIV infection as many of the drugs used to treat hepatitis B
4 (tenofovir, tenofovir and emtricitabine, lamivudine and entecavir) have activity against HIV and a
5 treatment regimen using only two drugs against HIV would not be considered standard of care.

7 **The risks and discomfort of percutaneous liver biopsy.**

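### The primary gene list is selected on an unadjusted p < 0.05, with a header that states the opposite threshold and an FDR that is estimated but cannot change the list

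*Combined protocol and SAP*

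**What the plan says.** The text is in the protocol's STATISTICAL ANALYSIS section, under Analysis methodology, steps c and d.

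- Header of step c: "A list of genes up- or down-regulated >2-fold with $p > 0.05$ will be prepared using the" procedure that follows.
- Sub-step 2 (pre-filter): "Lists will be prepared of genes that are up- or down-regulated >2-fold for any of the" subjects.
- Sub-step 3 (test): "A paired t-test will be used to identify genes from this list that have a p value < 0.05".
- Sub-step 4 (second filter): "The subset of the genes in (3) that are up- or down-regulated in >50% of patients in" certain groups, which are the "groups defined relapse and/or presence of cirrhosis will be identified".
- Sub-step 5: "This procedure will be repeated with $p < 0.01$, but the primary analysis will be" based on the p < 0.05 genes.
- Step d: "The false discovery rate (FDR) of the t test will be estimated". No method, target or action is attached.

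Three other places bear on this. Protocol Overview plans 60 patients, hence at most 60 biopsy pairs. Analysis methodology refers to microarray data, whereas Admission for pretreatment liver biopsy says that mRNA for ISGs, immune-cell markers and cytokines will be measured by real-time PCR or nanostring. Analysis methodology also calls itself a broad outline and promises a more detailed SAP before data analysis.

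**The concern.** The change in ISG expression between the two biopsies is part of the first primary endpoint, and the protocol justifies the second biopsy by it. The rule that decides which genes count as changed therefore matters.

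As written, the rule has three weaknesses. The header and the sub-steps give opposite thresholds. The operative threshold is a per-gene 5% level with no allowance for the number of genes tested. The FDR is computed afterwards and has no role in selection, so an estimate of 70% would leave the primary list unchanged. The 2-fold pre-filter looks like a safeguard, but with 60 patients it depends on the single most extreme value. If many genes are tested and few truly change, false genes could outnumber true ones.

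**Working it through.** The plan states no FDR, gene count, number of changed genes or SD, so there is no figure of its own to reproduce. From the documents: n = 60 pairs, two-sided paired t-test, thresholds 0.05 and 0.01. Assumed, and shown as ranges: genes assayed G, truly changed genes m1 (each changed 2-fold), and SD of the per-patient log2 difference, taken as normal and equal across genes.

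**1. Pre-filter (sub-step 2).** An unchanged gene exceeds 2-fold in one patient with probability q = 2Φ(−1/SD). It passes with probability f = 1 − (1 − q)^60. The table sets f beside r, the simulated probability (200,000 null genes per SD) that a null gene both passes and has p < 0.05.

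| SD | f | r | r / f |
|---|---|---|---|
| 0.3 | 0.050 | 0.0025 | 5.0% |
| 0.4 | 0.528 | 0.0261 | 4.9% |
| 0.5 | 0.939 | 0.0460 | 4.9% |
| 0.7 | 1.000 | 0.0502 | 5.0% |
| 1.0 | 1.000 | 0.0506 | 5.1% |

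The filter reduces the number of null genes tested only when the SD is small. Among those that pass, the error rate stays at about 5%.

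**2. Sub-step 3 list.** Expected false genes = (G − m1) × r. False share = false / (false + m1). All true genes are detected: at SD 0.5, t ≈ 1/(0.5/√60) = 15.5.

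| SD | G = 10,000, m1 = 300 | G = 20,000, m1 = 300 | G = 800, m1 = 100 |
|---|---|---|---|
| 0.3 | 24 false (7%) | 49 (14%) | 2 (2%) |
| 0.4 | 253 (46%) | 514 (63%) | 18 (15%) |
| 0.5 | 446 (60%) | 906 (75%) | 32 (24%) |
| 0.7 | 487 (62%) | 989 (77%) | 35 (26%) |
| 1.0 | 491 (62%) | 997 (77%) | 35 (26%) |

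These are expectations. Simulated lists scatter around them: about 6-15% at SD 0.3 for the two large arrays, and up to about 30% on the 800-gene panel.

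**3. Break-even.** More than half the list is false when m1 < 0.05·f·G / (1 + 0.05·f). With f = 1 this is 1,000/1.05 = 952 genes for G = 20,000, 476 for 10,000 and 38 for 800, or just under 5% of the genes tested. At SD 0.3 and G = 20,000 it falls to about 50.

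**4. Stricter repeat, p < 0.01, SD 0.5, m1 = 300.** G = 10,000: 9,700 × 0.94 × 0.01 = 91 false, 91/391 = 23%. G = 20,000: 19,700 × 0.94 × 0.01 = 185 false, 185/485 = 38%.

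**5. Sub-step 4.** Read as >2-fold in more than half of a group, it leaves the following null genes per 20,000, against about 920 (SD 0.5) and 1,012 (SD 1.0) at sub-step 3.

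| SD | group of 3 | 5 | 10 | 30 |
|---|---|---|---|---|
| 0.5 | 5 | <1 | 0 | 0 |
| 1.0 | 240 | 190 | 60 | 10 |

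On that reading it also removes true genes. One averaging exactly 2-fold exceeds 2-fold in each patient with probability 1/2, so in a group of 30 it is kept with probability P(at least 16 of 30) = 0.43, or about 128 of 300. Read instead as any change in one direction, sub-step 4 leaves about 860 of 906 false genes (20,000 genes, SD 0.5).

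**6. Selection on an FDR.** Benjamini-Hochberg at 5% holds the expected false share at 0.05 × (G − m1)/G. For m1 = 300 that is 4.85% (G = 10,000) or 4.93% (G = 20,000), about 15 false genes. Simulated runs kept all 300 true genes with roughly 14 to 23 false ones. Adding a requirement that the mean change be at least 2-fold would keep about half of genes truly at 2-fold (132-162 of 300 in simulation), because the sample mean falls below its true value half the time.

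**The case against.** A reader might infer that most genes on the primary list would be false, that the array is genome-wide, or that the ISG response could not be identified. The documents support none of these outright.

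- **Most genes false.** This depends on gene count, number of changed genes and SD, none of which is given. It fails at SD 0.3 in the scenarios above, on the 800-gene panel with 100 true genes, and on a 20,000-gene array if more than about 950 genes change.
- **Genome-wide.** The section speaks of microarrays, gene-array data and quantile normalization, which points to a large platform. The procedures section names PCR or nanostring, and no gene count appears.
- **ISG response lost.** In the scenarios run, the p < 0.05 list keeps every true gene. The Analysis plan correlates ISG levels with serological outcome and does not say that the ISGs come from this list. Sub-step 5 does call the list the basis of the primary analysis, so the link is unclear.

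It can also be said that sub-step 4 may remove nearly all null genes, that the header is an evident slip, and that an FDR estimate, a p < 0.01 repeat and a detailed SAP are promised. The first holds only if sub-step 4 means >2-fold and its groups number about 10 or more. The text states neither, and the groups are not the responder/non-responder contrast of the primary endpoint. The slip still needs correcting. The promised SAP does not displace a section that already names its primary threshold.

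**Conclusion.** The concern holds in a conditional form. Three points need no assumptions: the header contradicts sub-steps 3 and 5, primary selection is unadjusted, and the FDR has no role in it. It is also unclear whether the list from sub-step 3 or sub-step 4 is primary. That the any-patient filter leaves the per-gene error rate at about 5% holds at every SD tried, under a normal model.

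The size rests on assumed inputs. With 60 pairs, 300 genes truly changed 2-fold and SD 0.5 or more, the sub-step 3 list is about 60% false with 10,000 genes and 75% with 20,000. It is about 6-15% false at SD 0.3, and at most about 30% on an 800-gene panel with 100 true genes. The expected counts do not need independence between genes, but they do rest on normal differences and a common SD. This should be corrected before analysis. It does not show that the ISG analysis will fail.

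**What to change.** In Analysis methodology, or in the detailed SAP before data are analysed:

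1. Correct the step c header to p < 0.05.
2. Make the primary list the genes selected at a pre-stated FDR, for example Benjamini-Hochberg at 5%, from the paired test over all assayed genes. Drop the any-patient 2-fold filter and do not add a mean 2-fold requirement. Report fold change for ranking only.
3. State the sub-step 4 criterion (size and direction of change, definition of the groups) and which list is primary.
4. Reconcile the platform between Admission for pretreatment liver biopsy and Analysis methodology, and give the number of genes assayed.
5. Keep the unadjusted p < 0.05 and p < 0.01 lists as descriptive supplements.

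The cost is wording only: the p-values are already planned, and no patient, visit or sample is affected. The downside is a shorter primary list, with weak true signals moved to the descriptive lists.

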3. To identify pre- and on-treatment predictors of serological response to peginterferon add-on/nucleos(t)ide combination therapy.
4. To determine if there are differences in epigenetic regulation of cccDNA between HBeAg positive and negative CHB at baseline and following a single dose of peginterferon treatment

PROTOCOL OVERVIEW

We intend to enroll a total of 60 patients with HBeAg positive (n=30) and HBeAg negative (n=30) chronic HBV infection, who have been on-treatment with one or more nucleos(t)ide analogues for at least 192 weeks prior to study enrollment with maintained viral suppression (HBV DNA level <100 IU/ml). After a thorough medical evaluation and liver biopsy, participants will receive therapy with subcutaneous injections of peginterferon-alpha 2a at a dose of 180mcg per week for a total of 24 weeks. A second liver biopsy will be performed 6 hours following the first peginterferon injection for the purpose of assessing ISGs, intrahepatic NK cell quantity and function and intrahepatic viral biomarker response patterns. Most interferon induced genes achieve maximal response in the liver and periphery within 4 hours, begin to decline by 8 hours, and return to baseline levels by 24 hours post-administration of interferon. Because peginterferon is slower to be absorbed we have selected the six hour rather than a four hour time point.[38]

1 Patients will be followed carefully on weeks 0, 2, 4, 8, 12 and 24 during treatment and at 12 week
2 intervals thereafter until 48 weeks post-treatment.
3 During study visits patients will be assessed for compliance with study medications, as well as the
4 development of any treatment related side effects and/or adverse reactions. In addition, blood will
5 be drawn periodically for the assessment of routine blood tests, quantitative viral biomarker levels,
6 serological response markers and immune cell functional status.
7

8 **INCLUSION/EXCLUSION CRITERIA** 9

10 **Inclusion criteria: HBeAg positive group**

- 11
- 12 1) Age >18 years and older, male or female.
- 13 2) Known serum HBsAg and HBeAg positivity at the time of screening.
- 14 3) Ongoing treatment with one or more NUCs for at least 192 weeks before study entry.
15 Subjects may have a brief interruption of treatment for medical reasons (e.g. breast feeding)
16 not to exceed 8 weeks and none within the 48 weeks before study entry.
- 17 4) HBV DNA levels <100 IU/mL, measured at least 12 months prior to, and upon enrollment to
18 the study.

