23 peginterferon-alpha 2a (PEGASYS®, Roche), 180 mcg per week administered by subcutaneous
24 injection for a total of 24 weeks. Patients will continue treatment with their previous nucleosi(t)ide
25 analogue regimen during the treatment and follow-up phases of this study.

26 Patients will be seen in the outpatient clinic at weeks 2, 4, 8, 12, and 24, during treatment phase, at
27 12 week intervals thereafter up to 48 weeks post-therapy

28 Compliance will be monitored by medication diaries and counting of the residual vials returned at
29 outpatient visits. The side effects will be monitored regularly at each visit during the treatment phase
30 of the study by symptom questionnaires. Peginterferon alfa-2a will be dose reduced or stopped per
31 the dose reduction and stopping rules for peginterferon alfa-2a. Peginterferon alfa-2a treatment can
32 be restarted if the adverse event resolves and the patient is willing to re-start the medication.

33

34 **On-treatment liver biopsy**

35

1 At day 0, all patients will be readmitted to the NIH Clinical Center to start therapy with peginterferon
2 alfa-2a and to undergo a repeat liver biopsy. Biopsy will be scheduled at 6 hours following the first
3 injection of peginterferon, for the purpose of assessing ISG response pattern following the initial
4 exposure to peginterferon. Liver tissue will also be subjected to routine histopathological grading
5 and staging as well as for immune cell, quantitative viral kinetic and cccDNA epigenetic studies as
6 previously described.

7
8 Since the hypothesis to be tested in this study is that response to treatment peginterferon (i.e. loss of
9 HBeAg and HBsAg or both) is mediated by changes in hepatocyte gene transcription profile, it is
10 necessary to obtain liver tissue at two time points-before and 6 hours after the first dose of
11 interferon. Performing two liver biopsies within 12 weeks or even as short as 24 hours has been
12 performed in other Liver Disease Branch studies and has not been associated with an increase in the
13 complication rate or lower patient acceptance.

16 **Monitoring**

17 Day 0

- 18
- 19
- 20 1) Brief clinical evaluation
- 21 2) Review patient's eligibility for study
- 22 3) Symptom questionnaire
- 23 4) Visual analogue scale
- 24 5) Fatigue questionnaire (Promise 7)
- 25 6) Chemistry 20 (sodium, chloride, potassium, bicarbonate, calcium, phosphate, magnesium,

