32

33 **End of Add-on Peginterferon Treatment (Week 24 \pm 3 days)**

34 At week 24, all subjects will discontinue peginterferon alfa-2a add-on therapy (but continue the
 35 NUCs and undergo the following evaluation:

- 1 1) Physical examination
- 2 2) Symptom questionnaire
- 3 3) Fatigue questionnaire (Promise 7)
- 4 4) Visual analogue scale
- 5 5) Assessment of adverse events, concomitant medications and adherence
- 6 6) Blood will be drawn for Chemistry 20 (sodium, chloride, potassium, bicarbonate, calcium,
- 7 phosphate, magnesium, glucose, blood urine nitrogen, creatinine, uric acid, ALT, AST, LDH,
- 8 CPK, Alkaline Phosphatase, total and direct bilirubin, albumin, total protein), CBC
- 9 (hematocrit, hemoglobin, white blood cell count and differential, platelet count).
- 10 7) 50 mL of blood in heparinized green top tubes for NK and T cell analysis.
- 11 8) Urine tests: routine urinalysis and creatinine, phosphate and beta-2-microglobulin
- 12 9) HBV DNA viral load, HBeAg, anti-HBe, HBsAg, anti-HBs and quantitative HBe and HBs
- 13 measurement
- 14 10) Blood sample for storage (10 mL of blood separated into serum and plasma stored frozen in
- 15 0.5-1.0 mL aliquots)
- 16 11) Females of child bearing potential: Pregnancy test
- 17 12) TSH

18

19 **Post-treatment weeks 12, 24, 36 (\pm 5 days)**

- 20 1) Limited clinical evaluation
- 21 2) Symptom questionnaire
- 22 3) Visual analogue scale
- 23 4) Routine blood panel: Chemistry 20 (sodium, chloride, potassium, bicarbonate, calcium,
- 24 phosphate, magnesium, glucose, blood urine nitrogen, creatinine, uric acid, ALT, AST, LDH,
- 25 CPK, Alkaline Phosphatase, total and direct bilirubin, albumin, total protein), CBC
- 26 (hematocrit, hemoglobin, white blood cell count and differential, platelet count).
- 27 5) HBV DNA viral load, HBeAg, anti HBe, HBsAg and anti HBs levels
- 28 6) Blood sample for storage (10 mL of serum and 10 ml of plasma stored frozen in 0.5-1.0 mL
- 29 aliquots)
- 30 7) 50 mL of blood in heparinized green top tubes for NK and T cell analysis.

31

32

33 **Final study visit week 48 post-treatment (\pm 5 days)**

- 34 1) Limited clinical evaluation
- 35 2) Symptom questionnaire

- 1 3) Fatigue questionnaire (Promise 7)
 2 4) Visual analogue scale
 3 5) Routine blood panel: Chemistry 20 (sodium, chloride, potassium, bicarbonate, calcium,
 4 phosphate, magnesium, glucose, blood urine nitrogen, creatinine, uric acid, ALT, AST, LDH,

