21 interferon dosage. Another 5% of patients treated with interferon in our studies developed more
22 severe psychiatric side effects including paranoia, delusional thinking and marked anxiety. We have
23 found this side effect largely in patients with pre-existing psychiatric or neurological problems6.
24 These side effects reverse within one to two weeks after discontinuing interferon therapy.

25
26 Seizures may occur in patients receiving alpha interferon. These have been described as grand mal
27 seizures that were self-limited and stopped once interferon was discontinued. We have reported that
28 there is a 1-2% incidence of seizures during interferon therapy. These seizures occurred near the end
29 of therapy and did not recur. Several patients were hospitalized for the seizures and evaluated; no
30 abnormalities were detected on neurological examination or imaging studies, and none are currently
31 receiving anti-epileptic medication.

32
33 Neuropsychiatric: Life-threatening or fatal neuropsychiatric reactions may manifest in all patients
34 receiving therapy with interferon and may include suicide, suicidal ideation, homicidal ideation,
35 relapse of drug addiction, and drug overdose. These adverse effects occur in <1% of treated subjects.
36 These reactions may occur in patients with and without previous psychiatric illness.

1
2 Autoimmune phenomena: Development or exacerbation of autoimmune disorders including
3 myositis, hepatitis, thrombotic thrombocytopenic purpura, idiopathic thrombocytopenic purpura,
4 psoriasis, rheumatoid arthritis, interstitial nephritis, thyroiditis, and systemic lupus erythematosus
5 have been reported in patients receiving alpha interferon. These occur in less than 1% of patients.
6

7 **RISK/DISCOMFORTS IN RELATION TO BENEFIT**

8

9 **Protection against risks**

10 The risks of study medication regimen administration can be generalized into 3 areas, teratogenicity,
11 changes in hematological parameters, and non-specific side effects. To protect subjects from
12 teratogenicity, pregnancy tests will be performed every 2 weeks for the first 2 months, then every
13 month thereafter. Additionally, women should practice 2 forms of contraception. CBC's will be
14 performed every 2 weeks to monitor for hematologic changes, and symptoms or side effects will be
15 monitored at every visit, which may result in a study medication regimen dose modification. Another

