16 major risk to subjects who agree to participate in this study is the risk of undergoing 2 liver biopsies
17 (as outlined in Risks and hazards #3). Since a major endpoint of the study is to understand how
18 peginterferon may lead to HBeAg or HBsAg loss, the timing of the biopsies were chosen to maximize
19 our ability to demonstrate changes in interferon stimulated genes in the liver-up to 12 weeks before
20 and 6 hours after the first dose of peginterferon. Knowledge gained from this analysis may inform on
21 how best to use peginterferon in patients with chronic hepatitis B and identify new approaches to
22 induce HBeAg and HBsAg loss-highly desirable endpoints that may permit cessation of treatment.
23

24 **Potential benefits**

25 For patients with chronic hepatitis B, the strategy of add-on peginterferon offers a potential benefit
26 of loss of either HBeAg or HBsAg or both with the possibility of discontinuing all therapy and removal
27 of the risks associated with long term nucleoside analogue use-predominantly renal toxicity and
28 bone loss with tenofovir and cancer risk with entecavir. Thus, there is a prospect of overall clinical
29 benefit from participation in this study.
30

31 **DATA AND SAFETY MONITORING**

32

33 The adequacy of data acquisition and storage of samples and the monitoring of safety in this trial will
34 be performed by the principal investigator in collaboration with the associate investigators. Data and
35 safety are reviewed weekly in clinical research rounds by the Liver Diseases Branch, NIDDK. These
36 rounds are separate from regular clinical rounds and consist of review of all study patients including

1 flow sheets of major safety and efficacy measurements without knowledge of which therapy is used.
2 Monitoring of this study will also be conducted by the statistical department of NIDDK who will have
3 knowledge of the patient allocation. Reports of serious adverse events are made to the Clinical
4 Director NIDDK, and the IRB as outlined below.
5

6 **ADVERSE EVENT REPORTING**

7 **Definitions**

9

10 Protocol Deviation: Any change, divergence, or departure from the IRB approved research protocol.

11 Unanticipated Problem: Any incident, experience or outcome that meets all of the following criteria:

12 1. Unexpected (in terms of nature, severity or frequency) given (a) the research procedures
13 that are described in the protocol-related documents, such as the IRB approved research protocol

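### The risk section promises blood counts every 2 weeks and regular pregnancy tests, but the visit schedule has neither between weeks 12 and 24, and no text says which governs

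*Combined protocol and SAP*

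**What the plan says.** **Risk text.** Protection against risks (under Risk/Discomforts in Relation to Benefit) names three kinds of drug risk: teratogenicity, hematological change and non-specific side effects. For the first it says that "pregnancy tests will be performed every 2 weeks for the first 2 months, then every" month. For the second, CBCs are to be "performed every 2 weeks to monitor for hematologic changes", with no end date.

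**Schedule.** The Protocol Overview says "Patients will be followed carefully on weeks 0, 2, 4, 8, 12 and 24 during treatment". Initiation of Treatment says "Patients will be seen in the outpatient clinic at weeks 2, 4, 8, 12, and 24" during treatment. The Monitoring visit lists and Table 1 place a CBC and a pregnancy test at those visits and at day 0. They show no other on-treatment time point and no interim or local laboratory draw. At week 24, "all subjects will discontinue peginterferon alfa-2a add-on therapy".

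**Rules that use the counts.** Stopping peginterferon therapy (item c) requires the drug to be stopped for confirmed low platelets, hemoglobin or neutrophils. Table 2 sets dose reductions for neutrophils and platelets.

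**Oversight.** Data and Safety Monitoring says that data and "safety are reviewed weekly in clinical research rounds".

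**The concern.** The protocol justifies the risk to patients partly by tests that its own schedule does not provide. Staff work from the visit lists and Table 1. If they do so here, a patient can take peginterferon from week 12 to week 24 with no planned blood count and, where relevant, no planned pregnancy test. The dose-reduction and stopping rules for marrow suppression work only if a count is taken, and the week 24 count comes when the drug is stopped anyway. The weekly safety rounds do not close the gap, because no new scheduled count reaches them in that interval. What is at stake is patient safety and the accuracy of the stated safeguard, not the trial's inference.

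**Working it through.** **The plan's own figure.** Hazards and Discomforts says "Patients will have between 11 and 12 venipunctures" during the study. Scheduled visits with a blood draw are screening, biopsy admission and day 0 (3); weeks 2, 4, 8, 12 and 24 (5); and post-treatment weeks 12, 24, 36 and 48 (4). The total is 3 + 5 + 4 = 12, which agrees if the 6-hour and 24-hour draws around the first dose are not separate needle sticks (14 if they are). Two-weekly CBCs would add 7 draws: 12 + 7 = 19. The stated range therefore fits the visit schedule, not the risk text.

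**CBCs after day 0**

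| Reading of the two-weekly promise | Implied | Scheduled | Missing weeks |
|---|---|---|---|
| To week 24 | 12 | 5 | 6, 10, 14, 16, 18, 20, 22 |
| To week 12 only | 6 | 4 | 6, 10 |
| To week 8 only | 4 | 3 | 6 |

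Leaving out week 24, which cannot guide a dose, the count to week 24 is 11 implied and 4 scheduled.

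**The gap.** Successive intervals between scheduled counts are 2, 2, 4, 4 and 12 weeks. The last is 12 × 7 = 84 days, or 78 to 90 days with the ±3 day window at each end. Assuming one dose at each of weeks 0 to 23 (24 doses), the week 12 dose can use that visit's count. The doses at weeks 13 to 23 follow it: 23 − 13 + 1 = 11.

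**Pregnancy tests on treatment.** With 4-week months the promise implies weeks 2, 4, 6, 8, 12, 16, 20 and 24: 8 implied, 5 scheduled, with weeks 6, 16 and 20 missing. With calendar months (4.35 weeks) it implies weeks 2, 4, 6 and 8 plus about weeks 12.3–13.0, 16.7–17.4 and 21.0–21.7, which is 7. Taking week 12 to meet the first of the monthly tests, week 6 and two tests between weeks 12 and 24 are unmet on either reading.

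**What the counts could show, from figures in the protocol**
- Platelets: the entry floor is read as 70 × 10⁹/L and the largest quoted fall is 52%. 70 × (1 − 0.52) = 33.6, which lies in the Table 2 band for reduction to 90 µg. Reaching the stopping value of 25 needs a fall above 1 − 25/70 = 64.3%.
- Hemoglobin: the entry floors are 12 and 11 g/dL and the largest quoted fall is 5%. 12 × 0.95 = 11.4 and 11 × 0.95 = 10.45, both well above the stopping value of 8.5.
- Neutrophils: no baseline value is given, so no figure can be worked out.

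**Secondary point: neutrophils below 250/mm³.** The printed unit in the stopping rules is garbled. Read as 250/mm³, it equals 0.25 × 10⁹/L, the same threshold as in Table 2.
- Stopping peginterferon therapy, item c: once confirmed, treatment must stop.
- Table 2: interrupt until the count exceeds 1000/mm³, then restart at 90 µg.
- Item a of the same stopping section puts toxicity under the dose-modification table, so that table is operative. It cites the table as Table 1, but the title is that of Table 2.
- Peginterferon Dose Modifications calls the table a guideline, and Initiation of Treatment allows restart after an adverse event resolves.

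For platelets below 25 × 10⁹/L, by contrast, the two places agree.

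**The case against.** The strongest reply is that the risk text is itself protocol text. A reader might infer that the 12-week gap is an established fact of the design. The documents do not support that, because no sentence ranks the schedule above the risk section. If the risk text binds, there is no gap but an incomplete table. This limits the claim to what happens if sites follow the schedule. It does not remove the contradiction: even the shortest reading of the CBC promise leaves week 6 unmet, and the pregnancy-test promise has explicit timing.

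The safety weight is also limited. Four counts are scheduled by week 12, and patients are told to report fever. The protocol describes the marrow effects as rapidly reversible and says that serious bleeding has not been reported with interferon. The quoted hemoglobin falls come nowhere near the stopping value, and the platelet figure combines the lowest eligible baseline with the largest fall. Two forms of contraception are advised, and a suspected pregnancy must be reported at once. All of this stands, but none of it detects a silent fall in counts or an unsuspected pregnancy. The 72-hour repeat and the neutrophil monitoring after a restart reach only patients already found abnormal.

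Three further inferences are not supported. The venipuncture range is not shown to be wrong, since 12 visits fit it. Discontinuation is not shown to be the intended neutrophil rule: the guideline label points that way, while item a and the restart provision point the other way. Nor can a number of affected patients be given, because the timing of cytopenias is not stated.

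**Conclusion.** The two texts conflict and should be reconciled. This is an internal inconsistency about safety monitoring, worth fixing but not critical. If the schedule is followed, patients receive 5 post-baseline CBCs instead of 12 and, where applicable, 5 pregnancy tests instead of 7 to 8. No count that can guide dosing is scheduled after week 12, and 11 weekly doses follow that visit. These figures assume that the two-weekly promise runs to week 24 and that doses fall at weeks 0 to 23. Confidence is high for the mismatch. That a gap arises in practice depends on sites following the schedule, which the venipuncture range makes the likelier intention without proving it. The neutrophil conflict is a secondary matter of wording. No endpoint, sample size or analysis changes.

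**What to change.** 1. **Preferred.** Add a CBC and a urine pregnancy test between weeks 12 and 24, for example at weeks 16 and 20, as laboratory-only draws without the full content of an outpatient visit. Enter them in Table 1, the Protocol Overview, Initiation of Treatment and the visit lists. Weeks 16 and 20 match the monthly pregnancy tests already promised (4-week months). For CBCs they are a compromise that neither text states. The result is 7 counts after day 0, 6 of them able to guide dosing, and a longest gap of 4 weeks. Then rewrite Protection against risks to the actual schedule, so that it no longer claims two-weekly CBCs or a week 6 pregnancy test.
2. **Minimum.** Correct Protection against risks to the present schedule. This makes the text true but leaves the 12-week gap.
3. **Neutrophils.** State in both the stopping rules and Table 2 which action applies below 250/mm³, correct the unit and the table reference, and give the reason for the choice. The documents do not settle it.

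**Cost.** Amendment wording, two brief draws per patient (2 × 60 = 120 in all) and two urine tests per woman of childbearing potential. The stated venipuncture range would need updating, to 14 (or 16 if the 6-hour and 24-hour draws are separate sticks). Volume is no barrier. The protocol says the total "of blood drawn during an 8 week period will not exceed 10.5 ml/Kg or 550 mls", whichever is smaller. Any 8-week window containing week 16 or 20 holds at most three draws, so even at the 75 cc maximum the total is 3 × 75 = 225 mL. The per-kilogram limit would bind only below 225/10.5 = 21.4 kg.
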